# 7.4 Per Protocol Set (PPS), Immunogenicity Set

Per Protocol Set Persistence (24 months after last vaccination in V102\_15) – PPS Persistence (Day 1)

All subjects in the FAS Persistence who:

- Correctly receive all meningococcal vaccinations in the parent study (persistence objective) /all meningococcal vaccinations in the parent study and vaccinations relevant for the objective in the extension study (rest of immunogenicity objectives) and,
- Have no protocol deviations leading to exclusion (see section 8.3.8, Protocol Deviations) as defined prior to analysis and,
- Are not excluded due to other reasons defined prior to analysis (see section 8.3.8, Protocol Deviations).

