- Solicited AEs occurring at the day of each study vaccination and the following 6 days (6 hours post vaccination to Day 7) will be recorded daily using an electronic Diary (eDiary). The eDiary will incorporate instructions on how to assess reactogenicity grades and what data to be entered. The subject will be provided with a user guide to support use of the system.
- Unsolicited AEs occurring within 30 days (Day 1 to Day 31) after each study vaccination will be collected by a safety phone call 15 days after the vaccination and at the clinic visit 30 days after the vaccination by interviewing the subject and/or subjects' parents / guardian (as applicable) and by review of available medical records.

• Medically-attended AEs, AEs leading to study withdrawal and SAEs will be collected during the entire study period. These data will be captured by interviewing the subject and/or subjects' parents / guardian (as applicable) during the site visits and phone calls and by review of available medical records. Subjects and/or parents / guardian will be encouraged to call the site in case of any medically-attended AEs or any AEs which they perceive as being of concern during the entire study period. 6 months after the last vaccination the subjects and/or parents / guardian will be contacted by the site to collect any safety related information.

Immunogenicity assessments of the subjects will include:

Blood sample schedule: 3 samples for follow-on subjects—20 mL at Day 1, Day 6 (for follow-on) and Day 31. For naive subjects 4 samples of 20 ml each will be collected—at Day 1, Day 31, Day 66 and Day 91. All samples will be collected prior to vaccination.

Interim Analysis:

None planned. Data for all primary and secondary objectives will be analyzed and reported in a final CSR after primary testing and analysis are completed. Analysis of the exploratory objectives may be completed after primary analysis and the data reported in an addendum, depending on time of completion of serological testing for these objectives.

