3.5.1 Blood Specimens

A sample of approximately 20 mL sample of blood will be drawn from all follow on subjects at visits Day 1 before vaccination, and at visits Day 6 and **D**ay 31 and from all naive subjects at Visit Day1 before the vaccination and at visits Day 31, Day 66 and Day 91. The blood volume will not exceed 20 mL at each time point. A volume of 20 mL is

required in order to provide the necessary serum volume (approximately half of the blood draw volume) for the planned serology assays.

The blood will be used for immunological assays. See section 7., Assessments for additional details.

The total amount of blood collected over the study period per subject will be approximately 60 mL for follow-on subjects and 80 mL for naive subjects.

In order to minimize pain an anesthetic cream or patch (e.g. EMLA adhesives or cream) may be used at the site of blood sample draw, according to local practice. Not more than two attempts should be made to draw the required volume of blood.

The blood will be processed according to the Clinical Specimen Lab Manual and the serum will be distributed in aliquots using the tubes provided. All the aliquots will be stored at a temperature of -18°C or **below**. Each serum tube will be labeled with the labels provided by GSK. Serum samples will be sent to the sponsor or will be collected by a representative of the sponsor.

Complete instructions for labeling and storage of serum samples are included in the Clinical Specimen Lab Manual, which is stored in the investigator site file.

Testing of samples will be performed at GSK, Clinical Laboratory Sciences, Marburg, Germany or a delegate laboratory.

Samples will be retained in accordance with regulatory guidance for retention of essential study documents as described in section 10.

(Amended 4 April 2018)

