4. SELECTION OF STUDY POPULATION

4.1 Inclusion Criteria

Follow-on Participants

- Subjects from Finland and Poland previously enrolled in study V102_15 who have received all planned meningococcal vaccinations in the study¹
- Who have not received any additional meningococcal vaccination since the last meningococcal vaccination administered in the parent trial.
- Who have given written informed consent or assent (as applicable) after the nature of the study has been explained according to local regulatory requirements, prior to study entry. If the subject is under age 18 at the time of enrollment, the parent(s)/ legal guardian(s) of the subject should have given their written consent.
- Individuals of who the investigator believes can and will comply with the requirements of the protocol (e.g. use of an eDiary, return for follow-up visits, available for phone contacts).
- Individuals in good health as determined by the outcome of medical history, physical examination and clinical judgment of the investigator.

Naive Group

• Male and female individuals of similar age (approximately 12-20 years) to follow-on subjects from V102_15 trial.

- Who have not received any meningococcal vaccination since birth
- Individuals who have given their written informed consent or assent (as applicable) after the nature of the study has been explained according to local regulatory requirements, prior to study entry. If the subject is under age 18 at the time of enrollment, the parent(s)/ legal guardian(s) of the subject should have given their written consent.
- Individuals of who the investigator believes can and will comply with the requirements of the protocol (e.g. use of an eDiary, return for follow-up visits, available for phone contacts).

_

¹ Subjects will be eligible if they have received meningococcal vaccinations according to randomization assignment, irrespective of protocol-specified window.

• Individuals in good health as determined by the outcome of medical history, physical examination and clinical judgment of the investigator.

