# 6. DETERMINATION OF PROTOCOL DEVIATIONS

#### **6.1** Definition of Protocol Deviations

CSR reportable PD are defined in accordance with ICH E3 as important PDs related to study inclusion or exclusion criteria, conduct of the trial, subject management or subject assessment resulting in the potential to jeopardize the safety or rights of the trial subjects or the scientific value of the trial.

All reportable PDs will be evaluated before the analysis and classified according to ICH into the following five categories:

- Subject developed withdrawal criteria during the study but was not withdrawn
- Underlying medical condition forbidden by the protocol or which may influence immune response (PD code 240).
- Subject had contraindication for a subsequent study vaccination but was vaccinated (PD code 220).
- Concomitant infection related to the vaccine which may influence immune response (PD code 250).
- Subject received wrong vaccine or incorrect dose
- Study vaccine was not administered at all (PD code 100)
- Vaccine administration not according to protocol (PD code 140.x).
- Randomization failure (vaccination not according to randomization) (PD code 120).
- Subject took an excluded concomitant medication
- Administration of concomitant vaccine(s) forbidden in the protocol (PD code 150.x).
- Administration of any medication forbidden by the protocol (PD code 230.x).
- Subject randomized and did not satisfy the entry criteria
- Subject did not meet entry criteria (PD code 200).
- Deviation from key study procedures
- Subject did not comply with study vaccination schedule (PD code 140.x).
- Subject did not provide any post-vaccination unsolicited safety data (PD code 115.x).

- Subject did not provide any post-vaccination solicited safety data (PD code 116.x).
- Subject did not comply with blood draw schedule (PD code 270.x).
- Serological results not available post-vaccination (PD code 110.x).
- Obvious incoherence, abnormal serology evolution or error in data (PD code 112).

CSR reportable PDs will lead to exclusion of the subject or part of the subject's data from at least one analysis set.

The number of subjects in any and by PD category will be summarized by vaccine, center and overall. Individual subject listings will be provided in an appendix, sorted by subject and by PD category.

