## **6.2** Determination of Protocol Deviations

A set of listings will be provided to the Clinical Research and Development Lead (CRDL) and the Study Delivery Lead (SDL) for review according to SOP MON-11, on an ongoing basis during the study.

The listings will be programmed following the list presented in table in section 7.7, specifically using the PD codes specified in the first column.

After the review, the CRDL and the SDL will provide the Biostatistician with:

- An assessment of CSR reportable PDs based on blinded clinical data review.
- An assessment of subjects without PDs (e.g., premature withdrawals due to adverse event, withdrawal of consent) who should be excluded from an analysis set.

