110.d.502	Serology results are not available Serological results (A, C, W, Y and 4 B strains) are not available	Day 91			EXC (naive only)			EXC (naive only)
112.102	Obvious deviation from Laboratory Manual or error in laboratory data (HT-SBA)	Day 1				EXC		EXC
112.202	Obvious deviation from Laboratory Manual or error in laboratory data (HT-SBA)	Day 6 (follow on) Day 66 (naive)						EXC

PD code	PD Description	Study objective/ period	FAS IMM Persistence (Day 1)	FAS IMM (Day 31)	FAS IMM (Days 6, 31/Days 66,	PPS IMM Persistence (Day 1)	PPS IMM (Day 31)	PPS IMM (Days 6, 31/Days 66,
112.302	Obvious deviation from Laboratory Manual or error in laboratory data (HT-SBA)	Day 31			91)		EXC	EXC (follow on only)
112.502	Obvious deviation from Laboratory Manual or error in laboratory data (HT-SBA)	Day 91						EXC (naive only)
120.100	Randomization failure to treatment	Day 1				EXC (naive only)	EXC (naive only)	EXC (naive only)
140.100	Vaccination not according to protocol	Day 1				EXC	EXC	EXC
140.300	Vaccination not according to protocol	Day 61 (Naive only)						EXC (naive only)
150.100	Administration of forbidden vaccine	Day 1 (before BS_1)				EXC	EXC	EXC
150.300	Administration of forbidden vaccine	Day 1 (after BS_1)- day 7					EXC	EXC
150.500	Administration of forbidden vaccine	-7/+7 2 nd vaccination (naive only)						EXC (naive only)
200	Subject did not meet entry criteria	Day 1 – end of study				EXC	EXC	EXC

PD code	PD Description	Study objective/ period	FAS IMM Persistence (Day 1)	FAS IMM (Day 31)	FAS IMM (Days 6, 31/Days 66, 91)	PPS IMM Persistence (Day 1)	PPS IMM (Day 31)	PPS IMM (Days 6, 31/Days 66, 91)
220	Subject had contraindication for a subsequent study vaccination but was vaccinated	Day 1- Day 61 (naive only)						EXC
230.101	Administration of forbidden medication	Day 1				EXC	EXC	EXC
230.102	Administration of forbidden medication: ANTIBIOTICS	Day 1 (before BS_1)				EXC		
230.201	Administration of forbidden medication	Day 6 (follow on) Day 66 (naive)					EXC (follow on only)	EXC
230.202	Administration of forbidden medication: ANTIBIOTICS	Day 6 (follow on) Day 66 (naive)						EXC
230.301	Administration of forbidden medication	Day 31					EXC	EXC
230.302	Administration of forbidden medication: ANTIBIOTICS	Day 31 (before BS_2)					EXC	EXC (follow on only)
230.501	Administration of forbidden medication	Day 91						EXC (naive only)
230.502	Administration of forbidden medication: ANTIBIOTICS	Day 91						EXC (naive only)

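### SAP Table 7.7 drops Day 1 persistence titres from the per-protocol set for dosing errors that happen after the sample is drawn, and reaches parent-study dosing only through the entry-criteria code, which misses out-of-window and misadministered doses

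*SAP*

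**What the plan says.** SAP 7.4 requires members of PPS Persistence (Day 1) to "Correctly receive all meningococcal vaccinations in the parent study (persistence objective". Correct extension vaccination is added only for the remaining immunogenicity objectives, and Protocol 8.3.5 draws the same line. Neither document defines *correctly* for parent doses.

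The persistence sample comes before the extension dose. Protocol 3.5.1 has blood drawn from follow-on "subjects at visits Day 1 before vaccination, and at visits Day 6", with the naive Day 1 draw likewise before the dose. Protocol 3.1 adds: "All samples will be collected prior to vaccination".

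SAP Table 7.7 nevertheless marks two Day 1 vaccination codes as exclusions from PPS Persistence: 140.100, "Vaccination not according to protocol", for all subjects, and 120.100, "Randomization failure to treatment", for naive subjects. SAP 6.1 describes the latter as "Randomization failure (vaccination not according to randomization) (PD code 120"), so it concerns the vaccine actually given.

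On the parent doses, the footnote to Protocol 4.1 reads: "Subjects will be eligible if they have received meningococcal vaccinations according to randomization assignment, irrespective of protocol-specified window". SAP 6.2 ties the deviation review to the table: "The listings will be programmed following the list presented in table in section 7.7".

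**The concern.** The exposure whose persistence is being measured is the parent-study series. A per-protocol set for that question should screen that series and ignore what is done after the sample is taken. The table departs from this in two ways.

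First, an error in the Day 1 extension dose cannot alter a titre in blood already drawn. Removing the subject discards a valid primary observation. This includes naive subjects, whose Day 1 titre is a baseline whichever vaccine follows.

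Second, the condition that SAP 7.4 does impose has no code of its own. The primary objective names the 0,2-, 0,6- and 0,2,6-month schedules, and the study rationale asks whether a third dose gives lasting benefit. The full analysis set (FAS) keeps off-schedule parent dosing by design of the eligibility rule. If the PPS keeps it too, agreement between the two sets says little about whether off-schedule dosing matters.

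**Working it through.** The plan gives no figure to reproduce: Protocol 8.5 is marked not applicable and the primary objective has no hypothesis. The check is a comparison of passages plus a count of table cells.

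**1. Count.** The immunogenicity part of Table 7.7 has 36 code rows. Eleven exclude from PPS Persistence (PPS10FL): 110.100, 110.d.102, 112.102, 120.100 (naive only), 140.100, 150.100, 200, 230.101, 230.102, 240 and 270.100. Of these, 120.100 and 140.100 concern the extension dose.

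**2. Codes for events at or after the Day 1 dose.**

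| Code | Event (paraphrased) | PPS10FL, Persistence | PPS11FL, Day 31 | PPS12FL, Days 6,31/66,91 |
|---|---|---|---|---|
| 100 | No extension dose given | blank | EXC | EXC |
| 120.100 | Day 1 vaccine differs from randomisation | EXC (naive) | EXC (naive) | EXC (naive) |
| 140.100 | Day 1 dose not given per protocol | EXC | EXC | EXC |
| 150.300 | Prohibited vaccine after the first sample, to Day 7 | blank | EXC | EXC |
| 260.100 | Day 1 dose off schedule | blank | EXC | EXC |

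A subject never vaccinated in the extension keeps the Day 1 titre, while one given a wrong volume loses it. SAP 7.4 cannot support both. A Day 1 sample taken after the dose does not need 140.100, because 270.100 covers it (the table's footnote gives that example) and already excludes from PPS Persistence.

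**3. Parent-study doses.** Rows naming the parent study: 0. Every period is an extension-study day. Indirect cover by type of departure:
- Missed dose or wrong vaccine: fails the follow-on entry criterion, so code 200 excludes. Covered.
- Dose outside the parent window: expressly eligible under the Protocol 4.1 footnote, so code 200 does not apply. Not covered.
- Dose misadministered in volume, route or preparation: no entry criterion addresses it. Not covered.

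**4. Is the gap closed elsewhere?** SAP 7.4 refers to a section 8.3.8 on protocol deviations. The SAP has no such section. Protocol 8.3.8 leaves exclusionary deviations to the SAP. The cross-reference leads back to Table 7.7, and SAP 6.2 programs the listings from its codes.

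**5. Nesting.** SAP 7.4 makes PPS (Days 6,31/66,91) a subset of PPS Persistence. Code 230.102 (antibiotics before the first sample) is EXC in PPS10FL but blank in PPS12FL, so the coded sets already break that rule.

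**6. Illustrative size.** The documents give no rate of off-window parent dosing and no schedule effect. Assume a fraction *k* of a group is off schedule and each such subject differs by *d* on the log10 scale. The group GMT is then multiplied by 10^(k·d):
- k = 0.05, d = 0.2: 10^0.01 = 1.02, about 2%.
- k = 0.15, d = 0.3: 10^0.045 = 1.11, about 11%.

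Both inputs are assumptions. Giving every off-window subject the full *d* is generous, since some may be only days out.

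**The case against.** Several points on the other side have force.

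- **Parent dosing is not unscreened.** A reader might infer that Table 7.7 has no way to exclude incorrect parent vaccination. The documents do not support that: code 200 with Protocol 4.1 removes missed or wrong parent vaccines. This stands, and limits the gap to timing and administration.
- **Off-schedule subjects need not stay in.** The parent-vaccination condition in SAP 7.4 is separate from the condition on protocol deviations, so the lack of a code does not cancel it. SAP 6.2 lets reviewers exclude subjects without deviations, and SAP 6.1 requires a signed exclusion memo. This stands in part. The examples in SAP 6.2 are withdrawals, and nothing there is a rule for parent dosing. The condition is written but not made operational.
- ***Correctly* need not mean within window.** The only stated standard, for eligibility, is assignment irrespective of window. This is fair, and it is why the term needs defining. But if it meant no more than eligibility, the condition would add nothing to code 200.
- **Excluding misrandomised subjects is a stated rule.** SAP 4.1.1 excludes them from the PPS without exception. That is true, so 120.100 is not a slip in the table. The conflict is between SAP 4.1.1 and SAP 7.4, and both must be edited.
- **Code 140.100 may include timing.** SAP 6.1 puts both administration errors and schedule non-compliance under 140.x. For follow-on subjects, the Day 1 visit window of about 24 months (-1/+3 months) bears on persistence. However, Table 7.7 has 260.100 for the vaccination schedule, blank for persistence, and 270.100 for the blood draw. The overlap should be resolved in the text; it does not justify the present cell.

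**Conclusion.** The point holds in limited form. Codes 140.100 and 120.100 exclude from PPS Persistence for events after the sample, contrary to SAP 7.4 and Protocol 8.3.5 and out of line with codes 100, 150.300 and 260.100. Parent-study dosing is screened only through code 200, which does not reach out-of-window or misadministered doses.

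A reader might go further and conclude that the table inverts the SAP 7.4 definition, or that the per-protocol persistence result would be misleading. Neither is supported. Only two of the 11 excluding rows are at fault, one of them for naive subjects only. Whether the PPS is the only estimate of the named schedules depends on a reading of *correctly* that the plan has not fixed.

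The consequence is small. The FAS is the designated set, the PPS is a parallel analysis, and the primary objective has no hypothesis or success criterion. Each affected Day 1 dosing error removes one valid primary titre from the PPS, but the documents do not give the number of such subjects. The 2% to 11% shift rests wholly on assumed inputs and should not be cited as an estimate. The inconsistency itself needs no assumption beyond the sample preceding the dose, which the protocol states. It is cheap to correct and worth correcting.

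**What to change.** 1. **Table 7.7, extension dose.** Delete EXC from PPS10FL for 140.100 and 120.100, and keep it in PPS11FL and PPS12FL. Amend SAP 4.1.1 so that misrandomisation at Day 1 excludes from the post-vaccination PPS only. In SAP 6.1, state that 140.100 covers administration errors and that schedule deviations fall under 260.x.
2. **Table 7.7, parent doses.** Add a follow-on code for parent-study doses not given according to the assigned schedule or administration requirements in V102_15, with EXC in all three PPS columns. Define *correctly* in SAP 7.4 to match, by reference to the V102_15 protocol.
3. **SAP 7.4, nesting.** Define PPS (Days 6,31/66,91) as PPS Persistence plus correct extension vaccination, with its existing sample requirements. Reconcile 230.102 with that rule, and correct the reference to section 8.3.8.

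The cost is a table and text edit plus one merge with parent-study vaccination and deviation data. Follow-on subjects keep their parent Subject ID, so the merge is simple. The follow-on persistence PPS becomes somewhat smaller; by how much can be known only from the V102_15 data.

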#### Additional requirements:

Per Protocol Set Immunogenicity (Days 6 and 31, after booster dose [follow-on]/ Days 66 and 91 after second dose [naive]) – PPS Immunogenicity (Days 6, 31/Days 66, 91)

# All subjects in the PPS Persistence who:

• Provide evaluable serum sample with results for at least one serogroup B test strain or serogroups A, C, W or Y (only after MenABCWY vaccination) at each visit on Day 1, Day 6 and Day 31 (follow-on subjects) / Day 1, Day 66 and Day 91 (naive subjects) in the extension study.

PPS are subsets of FAS and should be always defined even if the objectives do not require it.

\_

<sup>5 Booster dose (follow-on) and first dose (naive in secondary objectives 2 and 4) / first and second dose (naive in secondary objectives 3 and 5).

Subjects might be excluded due to other reasons than protocol deviations (e.g., subjects who withdrew informed consent).

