8.3.5 Per Protocol (PP) Set Immunogenicity Set

Per Protocol (PP) Set Immunogenicity

All subjects in the FAS Immunogenicity who:

- Correctly receive all meningococcal vaccinations in the parent study (persistence objective) /all meningococcal vaccinations in the parent study and vaccinations relevant for the objective¹ in the extension study (rest of immunogenicity objectives) and,
- Have no protocol deviations leading to exclusion (see section 8.3.8, Protocol Deviations) as defined prior to analysis and,
- Are not excluded due to other reasons defined prior to analysis (see section 8.3.8, Protocol Deviations).

Additional requirements:

Per Protocol Set Immunogenicity (Days 6 and 31, after booster dose [follow-on]/ Days 66 and 91 after second dose [naive]) – PPS Immunogenicity (Days 6, 31/Days 66, 91)

All subjects in the PPS *Immunogenicity* who:

• Provide evaluable serum sample with results for at least one serogroup B test strain or serogroups A, C, W or Y (only after MenABCWY vaccination) at Day 1, Day 6 and Day 31 (follow-on subjects) / Day 1, Day 66 and Day 91 (naive subjects) in the extension study.

PPS are subsets of FAS and should be always defined even if the objectives do not require it.

¹ Booster dose (follow-on) and first dose (naive in secondary objectives *1* and *3*) / first and second dose (naive in secondary objectives *2* and *4*). Further details will be provided in the Statistical Analysis Plan.

Subjects might be excluded due to other reasons than protocol deviations (e.g., subjects who withdrew informed consent).

(Amended 4 April 2018)

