# Secondary Immunogenicity Objectives

- 1. To assess the immune response at Day 31 after a booster dose of the MenABCWY vaccine given 24 months after last meningococcal vaccination in subjects who previously received 2 or 3 doses of MenABCWY at different schedules (administered according to 0, 2-, 0, 6- and 0, 2, 6-month schedules) in study V102\_15 compared with the immune response at Day 31 after a single dose of MenABCWY in naive subjects, as measured by percentages of subjects with HT-hSBA titers ≥ LLOQ, percentages of subjects with four-fold rise² in titers and HT-hSBA GMTs against N. meningitidis serogroups A, C, W, Y and serogroup B test strains¹;
- 2. To assess the immune response at Day 1 (prevaccination), and at Day 6 and Day 31 after a booster dose of MenABCWY given at 24 months after last meningococcal vaccination in subjects who previously received 2 or 3 doses of MenABCWY at different schedules (administered according to 0, 2-, 0, 6- and 0, 2, 6-month schedules) in study V102\_15, and at Day 1 (prevaccination) and after 2 doses of MenABCWY (at Day 66 and Day 91) in naive subjects, as measured by percentages of subjects with HT-hSBA titers ≥ LLOQ, percentages of subjects

 Serogroup B test strains to be used in the study: NZ98/254 (PorA), M14459 (fHbp), M07-0241084 (NHBA) and 96217 (NadA).

<sup>2 For subjects with prevaccination hSBA titers < LLOQ, a post-vaccination hSBA  $\geq$  4 times the LLOQ; for subjects with prevaccination hSBA titers  $\geq$  LLOQ, an increase of at least 4 times the prevaccination hSBA.

with four-fold rise in titers and HT-hSBA GMTs against *N meningitidis* serogroups A, C, W, Y and serogroup B test strains;

- 3. To assess the immune response at Day 31 after a booster dose of the rMenB+OMV vaccine given 24 months after last meningococcal vaccination in subjects who previously received 2 doses of rMenB+OMV administered according to 0, 2-month schedule in study V102\_15 compared with the immune response at Day 31 after a single dose of rMenB+OMV in naive subjects, as measured by percentages of subjects with HT-hSBA titers ≥ LLOQ, percentages of subjects with four-fold rise³ in titers and HT-hSBA GMTs against *N. meningitidis* serogroup B test strains⁴;

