- 4. To assess the immune response at Day 1 (prevaccination), and at Day 6 and Day 31 after a booster dose of the rMenB+OMV vaccine given 24 months after last meningococcal vaccination in subjects who previously received 2 doses of rMenB+OMV at 0, 2-month schedule in study V102\_15, and at Day 1 (prevaccination) and after 2 doses of rMenB+OMV (at Day 66 and Day 91) in naive subjects, as measured by percentages of subjects with HT-hSBA titers ≥ LLOQ, percentages of subjects with four-fold rise³ in titers and HT-hSBA GMTs against *N. meningitidis* serogroup B test strains⁴.

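### SAP 7.4 footnote 5 maps naive dose requirements to superseded objective numbers, contradicting SAP section 2, protocol 8.3.5 and SAP Table 7.7; the effect is confined to the per-protocol analyses and is probably small

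*SAP*

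**What the plan says.** SAP 7.4 sets three cumulative conditions for the per-protocol sets: correct receipt of the required vaccinations, no excluding deviation, and no other pre-defined reason for exclusion. For all objectives except persistence, the first condition includes the extension-study vaccinations relevant to the objective. Footnote 5 says which these are. For naive subjects it gives "first dose (naive in secondary objectives 2 and 4"), and then "first and second dose (naive in secondary objectives 3 and 5").

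SAP section 2 lists four secondary immunogenicity objectives:

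- Objective 1: follow-on subjects "compared with the immune response at Day 31 after a single dose of MenABCWY in naive subjects".
- Objective 2: includes the response "after 2 doses of MenABCWY (at Day 66 and Day 91) in naive subjects".
- Objective 3: follow-on subjects "compared with the immune response at Day 31 after a single dose of rMenB+OMV in naive subjects".
- Objective 4: includes the response "after 2 doses of rMenB+OMV (at Day 66 and Day 91) in naive subjects".

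The protocol's footnote to 8.3.5 has the other mapping: "first dose (naive in secondary objectives *1* and *3"), with both doses for objectives 2 and 4. It refers the reader to the SAP for further detail.

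SAP Table 7.7 assigns each deviation code to analysis-set flags. PPS11FL is the Day 31 per-protocol set. PPS12FL is the set for Days 6 and 31 (follow-on) or Days 66 and 91 (naive).

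**The concern.** A per-protocol rule should ask for the doses that precede the endpoint and no others. Footnote 5 does neither for naive subjects. If followed, it would let subjects with one dose into results described as following two doses. It would also condition entry to the Day 31 rMenB+OMV comparison on a dose given at Day 61, after that endpoint has been measured.

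The first of these matters more. The full analysis sets require only that at least one study vaccination was received, so they already contain one-dose naive subjects by design. The per-protocol set is where receipt of both doses is meant to be enforced. If its dose rule is wrong, the per-protocol result stops being a clean two-dose result for the naive arms.

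**Working it through.** The plan states no figure on this point, so the check sets the passages side by side.

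**Step 1. Map each current objective to its rule for naive subjects.**

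| Secondary objective (SAP section 2) | Naive endpoint | Doses before the endpoint | SAP footnote 5 | Protocol 8.3.5 |
|---|---|---|---|---|
| 1 | MenABCWY, Day 31 | 1 | not mentioned | dose 1 |
| 2 | MenABCWY, Days 66 and 91 | 1 and 2 | dose 1 | doses 1 and 2 |
| 3 | rMenB+OMV, Day 31 | 1 | doses 1 and 2 | dose 1 |
| 4 | rMenB+OMV, Days 66 and 91 | 1 and 2 | dose 1 | doses 1 and 2 |
| 5 | does not exist | none | doses 1 and 2 | not mentioned |

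Footnote 5 gets none of the four right; the protocol gets all four right. The SAP numbers are the protocol numbers plus one (1+1=2 and 3+1=4; 2+1=3 and 4+1=5). Protocol Appendix A explains the shift: persistence moved from first secondary objective to primary, and the remaining secondary objectives each moved up one place. The SAP updated its list of objectives but not this footnote.

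**Step 2. Check which dose-2 problems Table 7.7 already handles.** Four codes concern the second vaccination: 140.300 (not given according to protocol), 150.500 (forbidden vaccine around it), 220 (contraindicated but vaccinated) and 260.200 (off schedule). All four exclude from PPS12FL only; none excludes from PPS11FL. Dose-1 problems (100, 120.100 for naive subjects, 140.100, 260.100) exclude from PPS11FL. That agrees with the protocol mapping and contradicts the footnote. PPS12FL also needs serum results at each of Days 1, 66 and 91 for naive subjects, so anyone who leaves before those visits is out whatever the footnote says.

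**Step 3. Find what is left.** Protocol 4.3 lists circumstances in which further vaccination must not be given, while encouraging the subject to stay in the study. For such a subject:

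- code 100 does not fit, because it also removes the subject from the Exposed Set, to which anyone who had dose 1 belongs;
- code 220 covers the opposite case;
- 140.300 and 260.200 describe departures from protocol, whereas withholding the dose here follows it.

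If the subject also gives Day 66 and Day 91 serum, the dose condition in 7.4 is the clearest text that would keep him or her out of PPS12FL, and footnote 5 sets that condition at dose 1.

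**Step 4. Size per subject.** With *k* one-dose subjects among *n* in a naive two-dose set, and response proportions *p2* (two doses) and *p1* (one dose):

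observed proportion = [(n − k)·p2 + k·p1] / n = p2 − (k/n)·(p2 − p1)

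Since p2 − p1 cannot exceed 1, the downward shift is at most k/n. With the planned 100 per naive arm and k = 1, that is 1/100, or one percentage point; slightly more if fewer than 100 are evaluable. The documents give no value for *k*, and do not say whether Day 66 and Day 91 blood is still drawn when dose 2 is withheld.

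**The case against.** The best defence is that the SAP already contains the right rule in the place that programmers will use. SAP 6.2 says the deviation listings are programmed from the section 7.7 table. SAP 6.1 requires a signed exclusion memo before analysis, and SAP section 16 has the exclusion file reviewed by a second programmer. The Day 31 per-protocol set has no text definition of its own in 7.4; it exists only as PPS11FL, from which no Day 61 deviation removes anyone. The larger per-protocol set is itself labelled as following the second dose. The reference to an objective 5 exposes the error at once. The full analysis set is the named set for the secondary objectives, and there are no hypotheses or success criteria.

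Most of this stands, and it limits the consequence. It does not remove the contradiction. The dose condition and the deviation condition in 7.4 are separate, and the table implements the second. A protocol-compliant omission of dose 2 is not clearly a deviation, so the table may not catch it. The SAP also commits to reporting every secondary objective on the per-protocol set as well, so two incompatible rules would face whoever checks the exclusion file.

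**Conclusion.** Footnote 5 is wrong as written; severity minor. It conflicts with the SAP's own objectives, the current protocol and the SAP's exclusion table. The practical exposure is narrow: per-protocol analyses only, and mainly naive subjects whose second dose was withheld as the protocol allows and who nevertheless supplied both later samples. Each would lower a two-dose percentage by at most about one point at 100 per arm. The number is unknown but expected to be small. If every missed second dose were coded as a deviation and only Table 7.7 were followed, the results would not change.

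Three stronger readings are tempting, and the documents do not support them:

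- A reader might infer that everyone who misses dose 2 would be kept in the two-dose set. The serum requirement and the dose-2 codes rule that out for most.
- A reader might infer that naive rMenB+OMV subjects will in fact be dropped from the Day 31 set for lacking dose 2. PPS11FL carries no such exclusion, and nothing says the footnote overrides the table.
- A reader might infer that both Day 31 comparisons require dose 2. Only objective 3 does on a literal reading; for MenABCWY (objective 1) the footnote is silent.

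**What to change.** Rewrite SAP footnote 5 with the mapping in protocol 8.3.5: the booster for follow-on subjects; for naive subjects, dose 1 for secondary objectives 1 and 3, and both doses for secondary objectives 2 and 4. Add one sentence saying that PPS11FL and PPS12FL implement this, so that a naive subject without a correctly received second dose, for whatever reason, is excluded from PPS12FL and never, on that ground, from PPS11FL. The cost is one footnote and one sentence in the SAP, made before the exclusion memo is signed. No protocol change and no new data are needed.
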